5. **Ethical committee approval:** Yes

6. **Study Methods**

Type 1 and 2 diabetic patients requiring intravitreal Anti-VEGF injections for treatment of center involving diabetic macular edema

Inclusion criteria:

1) Patients \geq 18 years old with type 1 or 2 diabetes mellitus with decreased BCVA due to diabetic macular edema and center involvement by the edema on spectral domain optical coherence tomography (SD OCT) with any stage of diabetic retinopathy

Exclusion criteria:

- 1) Ocular conditions that may affect macular perfusion (e.g. retinal vascular diseases, uveitis, vasculitis etc.)
- 2) History of vitreoretinal surgeries (excluding intravitreal injections)
- 3) Any previous treatment for diabetic macular edema
- 4) Presence of epiretinal membrane involving the macula or vitreomacular traction
- 5) Media opacity preventing good image quality
- 6) Uncontrolled glaucoma
- 7) Thromboembolic events within 6 months

Methodology in details

This is a prospective interventional study to evaluate the effect of repeated intravitreal injections of Anti-VEGF on macular perfusion in diabetic patients using optical coherence tomography angiography (OCTA).

Each patient will receive a detailed ophthalmologic examination including measurement of BCVA as well as applanation tonometry, undilated and dilated slit-lamp biomicroscopic examination and indirect fundus examination.

Duration of diabetes and its control through HbA1C measurement will be recorded for each patient.

Type 1 and 2 diabetic patients found to have BCVA worse than 6/6 and

clinical evidence of macular edema will undergo SD OCT and FA.

Patients with center involved macula edema detected by SD OCT will be included in the study and will undergo baseline macular OCTA.

These patients will then undergo intravitreal injections of Anti-VEGF monthly for 3 months then OCTA will be repeated to evaluate changes in macular perfusion and SD OCT will be repeated to assess retinal thickness. Patients with center involving macular edema on SD-OCT after the first 3 injections will continue to receive intravitreal Anti-VEGF injections monthly until the edema subsides or the study duration ends. These patients then undergo a final macular OCTA for perfusion evaluation and SD OCT for thickness assessment.

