OCTA will be performed with an Avanti RTVue XR system (Optovue, Inc., Fremont, CA, USA). Area of FAZ and capillary density at each capillary layer will be calculated before and after interventions using the OCTA machine software and ImageJ software.

All statistical analyses will be done using IBM SPSS v20.0 statistical software (IBM Corporation, NY, USA). Descriptive statistics will be calculated, and the data will be summarized as mean \pm SD for numerical data, and as frequencies and percentages for categorical data.

Possible Risk (mention if there is any risk or not)

Risk of cataract, glaucoma, endophthalmitis, retinal detachment, central retinal artery occlusion and vitreous hemorrhage

Primary outcomes

1- Effect of repeated intravitreal Anti-VEGF injections on Foveal Avascular Zone (FAZ) area and capillary density as a measure of macular perfusion change at different capillary levels in the macula.

Secondary outcome parameters

1- Effect of intravitreal Anti-VEGF injections on microaneurysms and vascular changes in the superficial and deep capillary plexuses of the macula using OCTA

2- Effect of intravitreal Anti-VEGF injections on choriocapillaris density using OCTA

3- Correlation of BCVA with degree of capillary non-perfusion before and after injections

Sample size (number of participants included)

50 eyes

Source of funding (is there any source of funds or not)

Self

7. Time plan

6 months from first injection

References:

1. Radwan S. Ajlan, Paolo S. Silva & Jennifer K. Sun (2016) Vascular Endothelial Growth Factor and Diabetic Retinal Disease, *Seminars in Ophthalmology*, 31:1-2, 40-48, DOI: 10.3109/08820538.2015.1114833
2. Early Treatment Diabetic Retinopathy Study Research Group. Photocoagulation for diabetic macular edema: Early Treatment Diabetic Retinopathy Study report number 1. *Arch Ophthalmol* 1985; 103:1796–806.
3. Regression of retinal and iris neovascularization after intravitreal bevacizumab (Avastin) treatment. *Retina* 2006; 26:352– 4.
4. Pegaptanib: a novel approach to ocular neovascularization. *Ann Pharmacother* 2006;40:1322– 6.

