**Cover Page**  
**Evaluation of the Effect of Intravitreal Injections**  
**of Anti-VEGF on Macular Perfusion in Diabetic**  
**Patients Using OCTA (IMPACT)**  
**NCT03246152**

**Document date: 5/16/2019**

**Upload date: 1/13/2020**

**Statistical methods:**

Data were coded and entered using the statistical package SPSS (Statistical Package for the Social Sciences) version 25. Data was summarized using mean, standard deviation, median, minimum and maximum in quantitative data and using frequency (count) and relative frequency (percentage) for categorical data. Comparisons between quantitative variables were done using the non-parametric Kruskal-Wallis and Mann-Whitney tests. For comparison of serial measurements within same patients paired t test was used in normally distributed quantitative variables while non-parametric Wilcoxon signed rank test was used for non-normally distributed quantitative variables (*Chan, 2003a*). Correlations between quantitative variables were done using Pearson or Spearman correlation coefficient (*Chan, 2003b*). Linear regression

analysis was done to predict changes in different parameters using baseline data (*Chan, 2004*). P-values less than 0.05 were considered as statistically significant.

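### The primary outcome is a set of unranked FAZ-area and capillary-density comparisons, each tested at an unadjusted 0.05 with no success rule, so the plan leaves open a false-positive rate above 5% if any one significant result is read as an effect

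*SAP*

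**What the plan says.** Under Primary outcomes (Protocol section 6) there is one item: the effect of repeated injections on "Foveal Avascular Zone (FAZ) area and capillary density as a measure of macular perfusion change at different capillary levels in the macula". The methodology text adds: "Area of FAZ and capillary density at each capillary layer will be calculated before and after interventions". Neither place lists the layers or puts one comparison ahead of another.

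The secondary outcomes help to fix the count. One concerns "microaneurysms and vascular changes in the superficial and deep capillary plexuses of the macula using OCTA". Another is "Effect of intravitreal Anti-VEGF injections on choriocapillaris density using OCTA", so the choriocapillaris is kept out of the primary set.

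OCTA is repeated after the first course: injections are given "monthly for 3 months then OCTA will be repeated to evaluate changes in macular perfusion". Patients whose edema persists continue treatment, and the text goes on: "These patients then undergo a final macular OCTA for perfusion evaluation". The final scan therefore appears to be limited to those who continue.

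The SAP (Statistical methods) states: "For comparison of serial measurements within same patients paired t test was used in normally distributed quantitative variables while non-parametric Wilcoxon signed rank test" for variables that are not normally distributed. It closes with "P-values less than 0.05 were considered as statistically significant". It mentions no adjustment, success rule or primary time point, and does not label any test exploratory.

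**The concern.** The protocol separates primary from secondary outcomes, which is sound. What is missing is control within the primary set. Several comparisons share primary status, each has its own 5% chance of a false positive, and nothing says whether one significant result is enough or all are needed.

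This matters because the protocol's background describes the existing evidence on anti-VEGF and macular perfusion as mixed in direction. In that setting a single significant layer or measure, for instance a change in deep-layer density alone, could be presented as settling the question. The plan as written does not rule that out, and a reader of the results could not tell whether such a finding was the planned test or the best of several.

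**Working it through.** The documents give no family-wise error rate and no derivation of the sample size, so there is no planned figure to reproduce. The only stated figure is the per-test threshold of 0.05.

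**Inputs from the documents**
- Threshold 0.05 per test (SAP, Statistical methods).
- Two primary measures, FAZ area and capillary density (Protocol, Primary outcomes).
- 50 eyes (Protocol, Sample size).

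**Assumptions**
- Two layers, superficial and deep. The background and a secondary outcome name these two, and the choriocapillaris is listed separately as secondary.
- Both measures taken in each layer, the natural reading of the methodology sentence: k = 2 × 2 = 4. If FAZ is a single area, k = 1 + 2 = 3.
- Two-sided tests (sidedness is not stated) and valid individual p-values.
- Correlations between the changes, which the documents do not give; a range is shown.
- Any single p < 0.05 is read as an effect.

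**Independent comparisons.** The chance of at least one false positive is 1 − (1 − 0.05)^k.
- k = 4: 1 − 0.95⁴ = 0.185
- k = 3: 1 − 0.95³ = 0.143

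**Common correlation r.** With c = 1.96, the chance is 1 − ∫ φ(u) [Φ((c − √r·u)/√(1−r)) − Φ((−c − √r·u)/√(1−r))]^k du, by numerical integration:

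| r | 4 comparisons | 3 comparisons |
|---|---|---|
| 0 | 18.5% | 14.3% |
| 0.5 | 15.6% | 12.5% |
| 0.7 | 13.0% | 10.9% |
| 0.9 | 9.4% | 8.4% |
| 0.99 | 6.3% | 6.0% |

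Simulated paired t tests with n = 50 agree at r = 0, 0.5 and 0.9 (four comparisons: 18.5%, 15.7%, 9.4%).

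**Block correlation.** A common r of 0.9 makes FAZ area as closely tied to density as one layer is to another. A less restrictive model lets layers of the same measure correlate more strongly than different measures do. For four comparisons:
- Layers 0.9, FAZ with density 0.3: 13.2% (simulation).
- Layers 0.5, FAZ with density 0: two comparisons correlated 0.5 give 9.07%, so the two independent pairs give 1 − (1 − 0.0907)² = 17.3%.

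**If all components must be significant.** The chance that every p-value falls below 0.05 when nothing changes cannot exceed the chance for any one of them, which is 5%. There is no inflation.

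**Effect of adjustment.** When nothing changes, Holm rejects something only if the smallest p-value is below 0.05/k, so its error then equals Bonferroni's. For k = 4 that is 0.0125. The family error is 1 − (1 − 0.0125)⁴ = 4.9% at r = 0 and 2.6% at r = 0.9.

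**Cost in power.** This is the detectable paired change in SD units of the change, from the noncentral t distribution with 49 degrees of freedom and noncentrality d√50, at 80% power:
- alpha 0.05: d = 0.404
- alpha 0.05/3 = 0.0167: d = 0.471
- alpha 0.05/4 = 0.0125: d = 0.488

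The last two are upper limits, because Holm relaxes the threshold after each rejection.

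**The case against.** The strongest reply is that the inflated rate belongs to a decision rule the documents never state. The objective is to study an effect, no hypothesis or success claim is written down, and the protocol's own statistical paragraph promises only descriptive summaries. Each comparison, read on its own, keeps a 5% error, and if all had to be significant nothing is inflated. This stands as a limit on the claim: the figures are conditional. It does not remove the gap, because the protocol declares a primary outcome, the SAP declares a significance threshold, and neither says how the two connect.

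A second reply is that the measures are strongly related. That lowers the rate, but it is still 9.4% for four comparisons at a common correlation of 0.9. It comes near 5% only when the comparisons are almost duplicates.

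A third is that the SAP is written in the past tense, so the tests may already have been run. That also stands in part: a family defined now cannot count as prespecified if results were known. Full reporting, intervals and adjusted p-values are still useful, and they would remove much of the harm even for a reader who prefers to treat the study as exploratory.

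A reader might infer two stronger things. One is that the study has an 18.5% error rate. The documents do not support this: the value needs independent measures, four comparisons and the any-one reading. The other is that the final OCTA doubles the primary set, giving 1 − 0.95⁸ = 33.7% if all were independent. No document makes that scan primary, it appears to cover only patients who continue, and repeated changes in the same eye are unlikely to be independent.

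**Conclusion.** The concern holds in a conditional form. It is certain from the text that the primary comparisons are unranked, that 0.05 is unadjusted and that no success rule exists. The size is not certain. With two layers and four comparisons at the OCTA after three injections, and only if any single p < 0.05 is taken as an effect, the false-positive chance is about 9.4% to 18.5% under a common correlation of 0.9 to 0, or 13.2% to 17.3% under the block model. With FAZ as a single area it is 8.4% to 14.3%. The layer count, the correlations and the any-one reading are all assumptions.

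A reader might also connect this with the sample being counted in eyes. The documents do not say that any patient contributes two, and the size of any such problem is a separate question that these figures do not measure. The point should be fixed because the remedy is cheap; it does not show that any particular result is wrong.

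**What to change.** In the SAP:
- Name the layers that count, and say whether FAZ area is measured in each.
- Make every FAZ-area and capillary-density comparison at the OCTA after three injections the primary family. That scan is scheduled for all patients.
- Apply Holm. For four comparisons, the ordered p-values are compared with 0.0125, 0.0167, 0.025 and 0.05 in turn, stopping at the first failure.
- Report every comparison with mean change, 95% CI, and raw and adjusted p-values, whatever the result.
- Report the final-OCTA comparisons in full as supportive. Keep the protocol's secondary outcomes secondary, and label all other tests exploratory.
- If the family was set after results were known, say so.

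Holm relies on valid raw p-values. If any patient contributes both eyes, use patient-level means or another test that accounts for the pairing.

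The cost is one paragraph and one results table, with no new data. With 50 independent eyes (assumed) and 80% power, the detectable change rises from 0.40 SD of the change to at most 0.49 with four comparisons, or 0.47 with three. The change cannot restore prespecification if the results are already known.
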